#### Week 53-55- OFF treatment follow-up

This visit is to be completed shortly after the last dose of study medication. This may be completed via phone or email.

• SLAES (monitoring for adverse events)

 All attempts will be made by study staff (and documented) to obtain all dispensed bottles of medication

## **PK Visits (Optional)**

In order to assess the PK (pharmacokinetic) properties of oxytocin, a select group of subjects who participate in the SOARS-B trial will be asked to participate in the PK study. Study staff will select the participants based on a) their willingness to participate and b) their ability to tolerate the study procedures. A total of 18 subjects will be enrolled across all 6 sites for the week 32 samples. There will be 6 subjects in each of the following age groups: 3-6, 7-12 and 13-17 years old. Each site will be asked to enroll one subject from each of the age groups. There will be a separate consent form for this optional study.

## Target Dose PK sample (48 IU TDD)

This visit may occur any time after week 32 (48 IU TDD)

This visit can be completed at any visit after week 32 or at an unscheduled visit

There will be a target of 6 participants in each age cohort total

if possible please also obtain vitals and PDDBI-SV and ABC.

#### Procedures are as follows:

- IV placement by study staff (saline solution only)
- Plasma oxytocin draw at T = 0 (time 0, immediately after insertion)
- Administration of intranasal oxytocin (target dose = 24IU but will be whatever dose the subject is currently prescribed to as part of the SOARS-B protocol)
- Plasma oxytocin draw at T = 15 minutes
- Plasma oxytocin draw at T = 30 minutes
- Plasma oxytocin draw at T = 45 minutes
- Plasma oxytocin draw at T = 60 minutes
- If feasible plasma oxytocin draw at T= 2-7 hours post dose
- Total blood volume = 42 mL (7mL per draw times 6 draws)

## Max Open Label Dose PK sample (72 IU TDD)

This visit may occur any time after the highest dose has been achieved (at an unscheduled visit or regularly scheduled visit)

The target is to have 2-6 participants receiving the 72 IU total dose, (at all sites) regardless of age If this is not occurring at a regularly scheduled visit, please also obtain vitals and PDDBI-SV and ABC.

#### Procedures are as follows:

- IV placement by study staff (saline solution only)
- Plasma oxytocin draw at T = 0 (time 0, immediately after insertion)

- Administration of intranasal oxytocin (target dose = 40IU BID)
- Plasma oxytocin draw at T = 15 minutes
- Plasma oxytocin draw at T = 30 minutes
- Plasma oxytocin draw at T = 45 minutes
- Plasma oxytocin draw at T = 60 minutes
- If feasible plasma oxytocin draw at T= 2-7 hours post dose
- Total blood volume = 42 mL (7mL per draw times 6 draws)

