## 5.2.1 Flexible Dose:

In the blinded phase, dosing will be flexible between 8/0 IU TDD and, after the target dose (48 IU TDD) has been maintained for  $\sim 7-8$  weeks, up to 80/0 IU TDD, to allow one to optimize dosing for the individual child in cases of intolerance or inadequate response. Doses will typically be given in two equal amounts in the AM and the PM, with the maximal dose at any one time being 48/0 IU. If doses are uneven the larger dose should be given in the AM.

In the open label phase, dosing will be flexible between 24 IU TDD and, after the target dose (48 IU TDD) has been maintained for  $\sim$ 7-8 weeks, the dose can be increased to 72 TDD at week 36. The

preferences is for 24 IU TDD to be given in the AM, 48 IU TDD should be split equally between morning and PM dosing and 72 IU TDD should be split as 48 IU in the AM and 24 IU in the PM.

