## **Suggested Titration to the Target Dose**

Blinded Phase: In the double-blind phase, titration to the target dose is expected to take 8 weeks and follow the suggested table below unless there are issues with tolerance or compliance. Dosing will begin at 8/0 IU in the AM at baseline. Typically, the dose will increase to 8/0 IU twice daily (BID) (16/0 IU TDD) at week 2. Dose will then be increased by 8/0 IU twice daily (BID) at weeks 4 and 8 with TDDs of 32/0 IU and 48/0 IU respectively. During the initial titration period (baseline to week 8), dosing increases should never occur before the time point specified in the schedule. Specifically one could not go to a TDD of 16/0 IU prior to week 2, or 32/0 IU prior to week 4 or 48/0 IU prior to week 8.

Week 0	Week 2	Week 4	Week 8
8 IU qD	8 IU BID	16 IU BID	24 IU BID
(8 IU TDD)	(16 IU TDD)	(32 IU TDD)	(48 IU TDD)

**Open Label Phase:** In the open-label phase, from week 24 to week 28, the dose will be 24IU in AM for a TDD of 24 IU. From week 28-36 the dose will be 48 IU TDD (ie. 24 IU BID). At week 36 the dose can be increased to 72 IU TDD (ie. 48 IU in the morning and 24 IU in the afternoon).

Week 24	Week 28
24 IU qAM	24 IU BID
(24 IU TDD)	(48 IU TDD)

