## **Optional Dose Reductions:**

In the blinded phase the dose may be reduced by 8/0 IU once or twice a day at any time at the clinician's discretion due to a clinically significant adverse event, poor tolerability of dosing, parent request. The dose should not be subsequently increased without reassessing the participant by phone/email or in person. The dose can be increased between scheduled visits after clinical reassessment of the participant (phone, email or in person). SLAES and CGI-I to be completed at physician discretion. If SLAES is not completed, then adverse events must be assessed and documented.

In the open-label phase the dose may be reduced in 24 IU increments to a minimum dose of 24 IU every other day.

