## **Dosing Increases Above Target Dose:**

In the blinded phase after the target dose has been maintained for at least 7 weeks the dose may be increased by 16/0 IU TDD only at each of the subsequent visits. Thus, at week 16, the maximal possible dose will be 64/0 IU TDD. However, at week 20 the dose could be increased to either 64/0 IU TDD if there had been no prior increase at week 16 or, could be increased to 80/0 IU TDD if the dose had been increased at week 16.

In the open-label phase after the target dose has been maintained for  $\sim$  7-8 weeks then the dose can be increased (at week 36) to 72 IU TDD.

**Applies to both phases:** Increases past the target dose are NOT required and may ONLY be made if the following conditions are met

- No evidence of clinically significant adverse events
- Parents agree
- Clinician agrees

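### The maximum open-label dose PK visit is headed 72 IU per day, but its procedure line gives 40 IU twice daily (80 IU per day), a dose described only for the blinded phase

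*Combined protocol and SAP*

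**What the plan says.** Protocol v6.0 describes two optional PK samples under PK Visits, one at the target dose and one at the highest open-label dose. The second is headed "Max Open Label Dose PK sample (72 IU TDD" and its recruitment aim reads "The target is to have 2-6 participants receiving the 72 IU total dose". The procedure list directly beneath gives the dosing step as "Administration of intranasal oxytocin (target dose = 40IU BID".

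The open-label dosing rules elsewhere in v6.0 agree with the heading:

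- Section 5.2.1 (Flexible Dose): "72 IU TDD should be split as 48 IU in the AM and 24 IU in the PM".
- Suggested Titration to the Target Dose, open-label part: "72 IU TDD (ie. 48 IU in the morning and 24 IU in the afternoon".
- Dosing Increases Above Target Dose, open-label part: "then the dose can be increased (at week 36) to 72 IU TDD".
- Section 5.2.4 (weaning): the rules start from 72, 48, 24 or less than 24 IU TDD. There is no entry for 80.

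The procedure list for the target-dose PK visit is worded differently. It names 24 IU but adds that the dose given "will be whatever dose the subject is currently prescribed to as part of the SOARS-B protocol". The maximum-dose list has no such clause.

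**The concern.** The heading and the dosing step of the same visit give different daily doses, both in current body text and not in an amendment log. No sentence in the PK section reconciles them. The figure sits in a procedure to be carried out in children, and it fixes the dose to which the PK samples will be attributed.

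Plasma is drawn at time 0, oxytocin is given, and draws follow at 15, 30, 45 and 60 minutes, with a later one if feasible. The samples therefore describe a single administration. If a site took 40 IU from the procedure line, the sample would not correspond to either dose of the 72 IU schedule that the visit is meant to characterise. With 2-6 participants, even one or two sampled at a different dose would affect what the sample shows.

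**Working it through.** **Inputs (all protocol v6.0)**

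- PK visit heading and recruitment aim: 72 IU TDD.
- PK procedure line: 40 IU BID.
- Open-label schedule (section 5.2.1; Suggested Titration): 48 IU morning, 24 IU afternoon, from week 36.
- Blinded-phase rule (Dosing Increases Above Target Dose): from the 48 IU TDD target, up by 16 IU TDD at week 16 and again at week 20.
- Table 3, not divided by phase: dose T = 40/32, dose U = 48/24, dose V = 40/40.

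**1. Reproduce the heading.** Morning + afternoon = 48 + 24 = 72 IU TDD. This matches the heading and is dose U.

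**2. Convert the procedure line.** 2 × 40 = 80 IU TDD, which is dose V. Difference: 80 − 72 = 8 IU per day; 8/72 = 11%.

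**3. Find where 80 IU TDD is permitted.** Blinded phase: 48 + 16 + 16 = 80 IU TDD. The open-label rules go no higher than 72, and the weaning rules do not provide for 80.

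**4. Check whether another 72 IU option explains the line.** Dose T gives 40 + 32 = 72, so a 40 IU administration can occur within a 72 IU total in Table 3. It is still not 40 IU twice a day, and the titration section sets the open-label 72 IU dose as 48/24. Dose T does not reconcile the two.

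**5. Compare as a single administration.** The documents do not say whether the morning or the afternoon dose is sampled, so both cases are shown.

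| Dose sampled | Scheduled | Procedure line | Difference | Relative |
|---|---|---|---|---|
| Morning | 48 IU | 40 IU | −8 IU | −8/48 = −17% |
| Afternoon | 24 IU | 40 IU | +16 IU | +16/24 = +67% |

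Neither case gives agreement.

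**The case against.** The best reply is that a careful reader will work out that 72 IU per day is meant. The visit takes place only once the highest open-label dose has been reached, it seeks participants already on 72 IU, and three dosing passages set that ceiling. Only one administration happens at the visit, so a twice-daily instruction cannot be carried out there. This stands, and it limits the consequences. It does not make the line correct.

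A reader might infer that sites would raise children to 80 IU per day. The documents do not support that: nothing in the PK section tells a site to change the daily dose. The 11% excess describes the wording, not a likely exposure. Nor does the text show a clear safety hazard, since 80 IU TDD is allowed in the blinded phase and lies within the overall 8-80 IU range of the Protocol Summary.

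A reader might also infer that the sampled dose would simply be 17% too low. That presumes morning sampling, which no section states. The week 36 and week 48 visit lists prefer plasma oxytocin draws between 2pm and 6pm, and the week 36 list lets the PK time-0 draw serve as that visit's plasma level. This does not settle the timing of the maximum-dose visit, which may be unscheduled, but morning sampling cannot be presumed.

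Two supporting arguments carry less weight than they may seem to. First, "In the open-label phase the dose may be reduced in 24 IU increments" governs reductions, not how a daily total is split, so the fact that 40 is not a multiple of 24 proves little. Section 5.2.1 also words its split partly as a preference; the titration section is the firmer ground. Second, the absence of a dose-recording step from the PK list is not specific to this error: the target-dose list has none either, and caregivers keep a diary of each dose given.

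**Conclusion.** The inconsistency is real and the procedure line is wrong as written: 80 IU per day against a stated open-label maximum of 72. As the single PK dose, 40 IU is 17% below the scheduled morning dose or 67% above the afternoon dose, depending on which is sampled. Those two figures assume the 48/24 split; the 8 IU per day discrepancy does not.

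The importance is low. The sub-study is optional, aims for 2-6 participants at this dose, and takes place in the open-label phase. The final SAP (section 2.3) leaves open-label analyses to separate plans, so the 24-week primary analysis, the sample size and the significance level are unaffected. The v6.0 change list records a new open-label dosing scheme, so the line may simply not have been updated; that is an inference, not something the protocol states.

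**What to change.** In the maximum-dose PK procedure list, replace the 40 IU BID figure with the participant's currently prescribed dose under the 72 IU TDD open-label schedule (48 IU morning, 24 IU afternoon), reusing the clause from the target-dose PK list. The cost is a one-line protocol correction.

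This wording leaves the time of sampling as it is. Fixing the sample to the morning dose, or adding a field for the single dose given, would be a further design choice and is not needed to remove the inconsistency.

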#### **Additional Risks for IV**

Most of the risks for IV insertion are the same as for venipuncture (bruising, pain, possible infection). Complications of gaining IV may include infiltration, hematoma, an air embolism, phlebitis, and intra-arterial injection. Infiltration is caused by the infusion of fluid outside the vesicles (vein), into the surrounding soft tissue. This is generally caused by poor placement of a needle outside of the vessel lumen. Clinically, you will notice swelling of the soft tissue surrounding the IV, and the skin will feel cool, firm, and pale. IV fluids are not dangerous to the surrounding soft tissues however certain medications can be toxic. We will not be administering any medications only IV fluids therefore this will not be an issue in our study. A hematoma occurs when there is leakage of blood from the vessel into the surrounding soft tissue. This can occur when an IV catheter passes through more than one wall of a vessel or if pressure is not applied to the IV site when the catheter is removed. A hematoma can be controlled with direct pressure and will resolve over the course of 2 weeks. An air embolism occurs as a result of a large volume of air entering the patient's vein via the IV administration set. Air embolisms are rare and easily prevented by making sure that all the air bubbles are out of the IV tubing before placement. Phlebitis is inflammation of the vein which occurs due to the pH of the agent being administered during the administration of the IV, since we are not placing any medications into the IV we will not be at risk for this complication. An intraarterial injection occurs very rarely. This can easily be prevented, by making sure that the needle is inserted in a vein. An experienced phlebotomist would not have an issue with the placement. If an artery is cannulated, there will be a pumping of bright red blood back into the angiocath, which would not be seen when you cannulate a vein. In the case of intraarterial injection, it is the intravenous drugs which pose severe problems, rather than the IV solution and since we will not be placing any drugs into the IV this will not be an issue for our study. In order to minimize these risks, we will ensure that all study staff that place the IV are well trained in proper procedures and use aseptic procedures.

## **6.5 Early Termination Visit**

If a subject terminates from the study early, then the following procedures should be completed as close as possible to the last dose. These procedures may be completed over the phone/email or in an office visit:

SLAES

- Suicidality assessment
- CGI-I/S
- Con Meds
- Psychosocial/Social Skills Therapy Logs
- Vitals (only if in office)
- Self-Rating of Social Functioning (only if in office)
- RMET (only if in office).

The questionnaires from the week 24 visit should be sent to the families and completed as close to the last dose taken as possible. If in open-label phase send week 48 questionnaires.

Any subject who is not able to return to the clinic or available for a phone call for an early termination visit within 2 weeks of their last dose will be considered lost to follow up no ET visit is required. All efforts should be made to retrieve the medication bottles from the families either mailed back or in person.

#### 6.6 Unscheduled Visit or Re-Evaluation Visit

Subjects may be asked to come in for an unscheduled visit at any time during the course of the study if the treating physician feels it is necessary to see the subject in person or to complete a PK visit. Subjects will be instructed to contact the site between scheduled visits if there are any issues that need to be addressed.

Subjects may also be re-evaluated with appropriate assessments completed for any of the following reasons:

- If the subject's dose is mandatorily reduced, then these assessments should be completed 2-4 weeks after the dose has been reduced.
- If the subject has had a CGI-I score of 6 or 7, then the assessments should be completed two-four weeks later at physician discretion.

During these visits, all efforts should be made to obtain the following assessments:

- Vital signs (only if in person visit)
- Review of concomitant medications
- SLAES (adverse events) and suicidality assessment
- CGI-S and CGI-I
- Focused Clinical Physical Exam (only if in person visit)
- If physician feels it is indicated, safety labs or ECG may be obtained.

#### **Unscheduled Assessments**

If the site learns that a participant's treatment has been interrupted for 1 week or longer, an unscheduled visit should be performed.

#### 7 STUDY PROCEDURES/EVALUATIONS

## 7.1 Study Assessments

#### **Parent Assessments**

Questionnaire Guidance Form: This form will give parents guidance on time frames and specific instructions for how to complete the questionnaires. This form was created by study staff with guidance from manuals from the standardized forms listed below.

Social Opportunities Questionnaire: This created form asks parents to rate how frequently their child has the opportunity to interact with different individuals in the community, home, school and daycare/after-school setting. It also asks, of those opportunities that their child has, does their child actually utilize those opportunities to interact with individuals in a social manner.

Social Reciprocity Scale-2: This 65-item rating scale measures the severity of autism spectrum symptoms as they occur in natural social settings (Constantino, Davis et al. 2003). Completed by a parent or teacher in just 15 to 20 minutes, the SRS provides a clear picture of a child's social impairments, assessing social awareness, social information processing, capacity for reciprocal social communication, social anxiety/avoidance, and autistic preoccupations and traits. It is appropriate for use with children from 4 to 18 years of age. The SRS measures impairment on a quantitative scale across a wide range of severity--which is consistent with recent research indicating that autism is best conceptualized as a spectrum condition rather than an all-or-nothing diagnosis. The SRS-R will take the parent/caregiver/LAR approximately 10 minutes to complete.

Pervasive Developmental Disorders Behavior Inventory (PDDBI-Screening Version) - The PDDBI-SV examines both adaptive and maladaptive behaviors related to social behaviors in autism. It is a parent/caregiver questionnaire and has 18 items. It takes about 5-10 minutes to administer.

Aberrant Behavior Checklist (ABC)-The ABC focuses on problem behaviors in five subdomains: irritability, attention, repetitive behaviors, unusual speech, and social withdrawal. This should take the caregiver approximately 10 minutes to complete.

Caregiver Strain Questionnaire (CSQ – Berument): The CSQ will assess family stress and was developed for caregivers of children with developmental disabilities. This should take the caregiver approximately 5 minutes to complete.

*Medication Diary:* Caregivers will be asked to record each dose given to the child on a written log. Caregivers will be asked to return this at each visit for the study team to review if there are any medication compliance issues.

Parent Handout (Risks): Caregivers will be given an informational handout at baseline (beginning of Randomized Phase) and again at week 24 (beginning of Open Label Phase). This handout will describe possible symptoms to look for.

Dosing Guide/Medication Administration Form: Caregivers will be given an informational handout that describes study drug administration and dosing guidelines. Participants will be instructed to increase the dose per the titration schedule as long as there are no problems and will be strongly encouraged to contact the study coordinator if there are any concerns.

Vineland Scales of Adaptive Functioning (2nd edition, Parent/Caregiver Rating Form): The VABS-II is a survey administered to a parent or caregiver in a questionnaire format and is organized around four Behavior Domains: Communication, Daily Living Skills, Socialization, and Motor Skills. The

VABS-II will take the parent/caregiver/LAR approximately 20-60 (average 30) minutes to complete, depending on the subject's age and level of functioning. For the purposes of this study, we will not be assessing maladaptive behaviors.

Childhood Anxiety Sensitivity Index (CASI-5): This scale is designed for measuring anxiety sensitivity (i.e., the belief that anxiety symptoms have negative consequences. There will be one form that is for children ages 3-4 and a different one for ages 5-17.

## Physician/Clinician Assessments

Clinical Global Impressions Scale: Overall psychiatric functioning will be assessed with the severity (CGI-S) and improvement (CGI-I) subscales of the CGI (Guy 1976). CGI-S items are rated from 1 (normal, not ill) to 7 (very severely ill). CGI-I items are rated from 1 (very much improved) to 7 (very much worse).

Physical Examination: A physical examination can include, but is not limited to, abdominal palpation to assess for liver enlargement, assessing for decreased tone and postural problems, increased drooling and poor orofacial tone, problems holding head up as well, difficulty with coordination of motor actions. A more thorough exam will be done at screening and a more brief/clinician focused one completed at subsequent in person visit.

Concomitant Medication Log: At screening, the physician will make a list of any medications the subject is currently taking (ie: on the day of screening). The physician will record any changes to the subjects' psychiatric and non-psychiatric medications from screening throughout the course of the study. PRNs will not be recorded unless:

they are taken for a period of 2 weeks or more AND they are taken more than 57% of the time (ie: 9 out of 15 days)

OR

the clinician feels there is a compelling reason to document them in which case this can be documented in a note to file. Example: a PRN that is used to address an AE may be noted directly on the SLAES form for clinician reference in the future, but will not be data entered.

*Inclusion/Exclusion:* A checklist will be completed to ensure all inclusion and none of the exclusion criteria are met.

DSM-V Checklist for Autism: The proposed DSM-V criteria for autism will be documented in the form of a checklist for a clinician/physician to complete.

Family Medical History: This form will ask for information about genetic, mental health and medical conditions of relatives of the subject.

*Medical History:* This form will ask about the subject's medical history such as surgeries, medical procedures etc.

Oxytocin Dosing Log: This log is completed by the physician to record all changes in dosing of oxytocin. It will include start/stop dates of when the dose changes.

